## **SUMMARY**

The goal of this prospective, post-market study is to measure AEON™ Endostapler performance for laparoscopic bariatric surgery against the Endo GIA™ Reloads with Tri-Staple™ Technology from Medtronic. Stapler performance will be evaluated primarily by incidence and degree of staple line bleeding from endoscopic images, evaluated by a blinded third-party. The study will include 60 total consecutive cases of individuals undergoing a planned laparoscopic sleeve gastrectomy (LSG). The LSG procedure will be performed according to institutional standard-of-care and all subjects will undergo standard preoperative evaluation as well as post-operative care. Relevant data will be collected using the Data Collection sheet which should be filled out following each procedure by a member of the surgical or nursing team.

**Enrollment:** 60 Subjects Meeting Inclusion/Exclusion Criteria

**Investigator Masking:** None (Open Label)

**Primary Outcome Evaluator Masking:** Yes (Surgeon and Device)

**Devices:** AEON™ Endostapler and Endo GIA™ Reloads with Tri-Staple™ Technology and Ultra Universal Handle

## BACKGROUND

The AEON™ Endostapler is comprised of a stapler handle and reloads. The handle may accept multiple reloads of single fire cartridges. The AEON™ Endostapler devices were approved by the United States Food and Drug Administration (FDA) under the 510(k) process. Pertinent applications numbers are K171589 and K173443. Devices will be used pursuant to the indications specified in K171589 and K173443, as well as the general guidelines for use of this device on a prescription basis as outlined by the Federal Food, Drug, and Cosmetic Act (1976), and the Code of Federal Regulations Title 21 Part 800-895.

## Approved Indications for Use

The AEON™ Endostapler has applications in general, abdominal, gynecologic, pediatric and thoracic surgery for resection, transection and creation of anastomoses.

## Available AEON™ Endostapler Reloads

The following two tables contain the available AEON™ Endostapler Reloads, as well as the similar products that they may replace. This is meant as a guide, and the surgeon should read and follow the Instructions for Use and use their own clinical judgment to determine appropriate products to use.

*Table 1. Available AEON™ Endostapler Reloads*

Reload Type	Cartridge Length	Product Code	Open Staple Height	Closed Staple Height	Minimum Port Size
Gray	45mm	AESR45G	2.0mm	0.75mm	12mm
White	45mm	AESR45W	2.5mm	1.0mm	12mm
White	60mm	AESR60W	2.5mm	1.0mm	12mm
Orange	45mm	AESR45R	3.25mm	1.5mm	12mm
Orange	60mm	AESR60R	3.25mm	1.5mm	12mm
Purple	45mm	AESR45P	4.0mm	1.8mm	12mm
Purple	60mm	AESR60P	4.0mm	1.8mm	12mm
Black	60mm	AESR60B	5.0mm	2.2mm	15mm

*Table 2. Approximate Equivalence for AEON™ Endostapler Reloads*

AEON™ Endostapler			Endo GIA™ with Tri-Staple™ Technology		
Cartridge Color	Open Staple Height (mm)	Closed Staple Height (mm)	Cartridge Color	Open Staple Height (mm)	Closed Staple Height (mm)
Gray	2.0	0.75	Gray	2.0	0.75
White	2.5	1.0	Tan	2.0-3.0	0.75-1.25
Orange	3.25	1.5	Purple	3.0-4.0	1.25-1.75
Purple	4.0	1.8	Purple	3.0-4.0	1.25-1.75
Black	5.0	2.2	Black	4.0-5.0	1.75-2.25

## **STUDY DETAILS**

Patients will be screened based on the inclusion and exclusion criteria below and will be consecutively evaluated for study enrollment. Each case will be randomly assigned to one of the two FDA approved endoscopic staplers. For the purposes of this study, the surgeons will either use the AEON™ Endostapler or the Endo GIA™ Reloads with Tri-Staple™ Technology and Ultra Universal Handle from Medtronic. Enrollment will be contingent on meeting these criteria, and the use of either the AEON™ Endostapler or the Endo GIA™ Reloads with Tri-Staple™ Technology from Medtronic. Study participation will begin once the subject signs the consent form and will end after the one-month postoperative follow up visit.

### **Selection of Subjects:**

#### **Inclusion Criteria**

- Patients undergoing planned laparoscopic sleeve gastrectomy
- Informed consent for study obtained and signed from each subject

#### **Exclusion Criteria**

- Planned open surgical approach
- Use of staple line reinforcement material (butress)
- Revision or other bariatric procedure
- Patients with a bleeding disorder: known coagulopathy, or Platelets <100,000, or PTT > 45sec, or PT > 15sec, or INR > 1.5
- Patients with active HIV or Hepatitis B
- Patients under the age of 18 on the date of the surgery
- Patients who are pregnant
- Patients using tobacco products within the last 2 weeks prior to surgery date
- Patients using cortisone or related products within the last 2 weeks prior to surgery date

### **Withdrawal of Subjects:**

Subjects are free to withdraw from the study at any time for any reason. Every effort will be made to determine why any subject withdraws from the study prematurely and this information will be recorded in the Clinical Study Report.

In addition, subjects may be withdrawn from the study by the Principal Investigator in consultation with the Sponsor for the following reasons:

- Adverse event
- Protocol violation
- Loss to follow-up

If a subject withdraws prematurely, all data normally collected by study completion should be collected at the time of premature discontinuation or at the scheduled discharge. All subjects who withdraw from

the study with an ongoing adverse event must be followed until the event is resolved or deemed stable. At the discretion of the PI, additional follow up visits may be done for subject safety.

Withdrawn subjects will be replaced, until 60 subjects complete the study.

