**Secondary Outcome Measures:**

- Incidence of postoperative leakage requiring intervention through 30-day post-operative evaluation period
- Incidence of intraoperative or postoperative blood transfusion within 72 hours of surgery start time
- Hemoglobin difference between preop hemoglobin and hemoglobin on postoperative day #1 as well as difference between hemoglobin at recovery room and postoperative day #1
- Incidence of reported device-related adverse events through 30-day post-operative evaluation period
- Incidence of product malfunction during stapling
- Total hospitalization time
- Postoperative pain level per standard protocol (0-10 VAS scale completed at Recovery room, 6hrs postop and 7am at POD#1)
- Postoperative nausea presence (0-10 scale VAS completed at Recovery room, 6hrs postop and 7am at POD#1)
- Incidence of vomiting: incidence (at least one per patient) per stapler group, total episodes per group and emesis material (bloody or non-bloody)
- Correlation of number of reloads used and specimen lengths and maximum widths as measured by pathology examination
- Correlation of reload color used with observed bleeding and patient's stomach thickness by path exam
- Correlation of outcome parameters with BMI, visceral fat, gender and age
- Need for clipping the staple line prior to completion of the staple line

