Gastroscopy will be performed, per standard protocol, at the beginning of the case to suction all gastric contents and decompress the stomach as well at the completion of the sleeve gastrectomy. Evaluation for intraluminal bleeding will be performed at the last gastroscopy according to Appendix E. During the last gastroscopy, no suctioning of the gastric contents will be performed until evaluation for bleeding is made and pictures are obtained. The gastroscopy will be performed before any use of clipping at the staple line unless for circumstances judged by the surgeon to be medically necessary to do so before the endoscopy. These instances will also be recorded. Five pictures will be obtained from each case: the pylorus, distal sleeve near the distal end of the staple line, mid-sleeve at the incisura angularis, proximal sleeve and GEJ near the proximal end of the staple line. These photographs will also be sent to the third-party evaluator for evaluation of staple line bleeding according to a provided Bleeding Severity Scale for Endoscope Images (Appendix B). Results will be recorded in the Bleeding Severity Evaluation Sheet (Appendix E).

The determination of laparoscopic and endoscopic staple line bleeding will be based on the picture with the highest bleeding severity score for laparoscopic and endoscopic evaluation separately. Every effort will be made that all pictures prior to any suctioning of the staple line laparoscopically or endoscopically.

All typical post-operative care will continue, including immediate post-operative care prior to hospital discharge as well as the standard post-operative evaluation. A hemoglobin level will be checked at the

recovery room and at 5am on postoperative day #1 per standard protocol. This hemoglobin must be drawn from the upper extremity opposite from the one with the IV running fluids or at the same extremity with the IV running fluids but distal to the IV. For each post-operative period, a member of the surgical or nursing team will fill out the relevant sections of the Data Collection Sheet (Appendix C).

There will be no follow up study data collected after this point, however the patients will continue the standard follow up regimen per the physician's practice.

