### Intraoperative Outcomes

Product malfunction during stapling? (circle one)	Yes	No
Blood transfusion due to staple line bleeding? (circle one)	Yes	No
Visceral fat:		
Clips required for bleeding (non-routine)? (circle one)	Yes	No

*If yes to any above, please specify:*

Postoperative Outcomes				
	Pre-op	Recovery	6 Hours	POD #1
Pain level per standard protocol (0-10 VAS scale):	N/A			
Nausea level per standard protocol (0-10 VAS scale):	N/A			
Hemoglobin:			N/A	
72 Hours				
Blood transfusion due to staple line bleeding? (circle one)	Yes		No	
30 Days				
Total hospitalization time:				
Number of vomiting episodes:		Bloody	Non-bloody	
Reported device-related adverse events? (circle one)	Yes		No	
Postoperative leakage requiring intervention? (circle one)	Yes		No	

*If yes to any above, please specify:*

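### Thirty-day leak and device-event status may be recorded at withdrawal or discharge on an undated Yes/No form, so early withdrawals could be counted as event-free at 30 days or dropped from the rates

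*Combined protocol and SAP*

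**What the plan says.** Secondary Outcome Measures defines the leak outcome as "Incidence of postoperative leakage requiring intervention through 30-day post-operative evaluation period" and gives device-related adverse events the same window. Under Study Details, participation "will end after the one-month postoperative follow up visit".

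For premature withdrawal, Withdrawal of Subjects directs that "all data normally collected by study completion should be collected at the time of premature discontinuation or at the scheduled discharge". The listed reasons include adverse event and "Loss to follow-up". Required follow-up after withdrawal is limited to subjects leaving "the study with an ongoing adverse event must be followed until the event is resolved or deemed stable"; further visits are at the investigator's discretion. The section ends: "Withdrawn subjects will be replaced, until 60 subjects complete the study".

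In the 30-day block of Appendix C, the leak item reads "Postoperative leakage requiring intervention? (circle one", with Yes and No as the only choices. The device-event item has the same two choices. Neither has an assessment date or a category for status not known.

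Steps and Procedures has the data sheet filled in for each post-operative period, and then has this sentence, cut here before its last word: "There will be no follow up study data collected after this point, however the patients will continue the standard follow up regimen per the physician's". The Statistics section defines no analysis set, no missing-data rule and no handling of withdrawn subjects.

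**The concern.** The withdrawal rule moves the collection of end-of-study data forward to exit or discharge. For most items that is harmless. For an outcome defined over 30 days it changes what is measured: status when last seen takes the place of status at day 30. A form with two choices and no date cannot show which of the two was recorded.

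Loss to follow-up makes this sharper. A subject declared lost usually cannot be assessed at that moment, so discharge may be the only available source for the 30-day entry. A leak that first appears after withdrawal has no required route into the data.

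What is at stake is the credibility of two safety rates. Under-counting makes each device look safer. If it is similar in both arms, it also narrows the absolute difference between them, which is the unhelpful direction in a study whose stated purpose is non-inferiority.

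**Working it through.** The plan gives no leak rate, withdrawal rate, margin or power for this point, so there is no figure of its own to reproduce beyond the allocation, 30 + 30 = 60. The check is mainly of the text, followed by an illustration of size.

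**Text.** The two outcomes run to 30 days and participation runs to one month. The withdrawal rule allows collection at exit or discharge, either of which can fall well before day 30. The form cannot separate event-free through day 30 from event-free when last seen. For a hypothetical patient last seen on postoperative day 2, the observed share of the window is 2/30 = 7%.

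**If withdrawn subjects are analysed.** Let *p* be the true 30-day risk, *w* the share of analysed subjects last seen early and recorded as No, and *s* the share of events that fall after last contact. All three are assumptions: *p* = 1% to 5%, *w* = 3% to 20%, *s* = 50% to 100%.

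- Observed risk = *p* × (1 − *w* × *s*)
- Expected missed events per arm = 30 × *p* × *w* × *s*

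| *p* | *w* | *s* | Observed risk | Missed per 30-patient arm |
|---|---|---|---|---|
| 1% | 3% | 50% | 0.985% | 30 × 0.01 × 0.03 × 0.5 = 0.0045 |
| 3% | 3% | 50% | 2.96% | 0.013 |
| 3% | 10% | 80% | 2.76% | 0.072 |
| 3% | 20% | 100% | 2.40% | 0.18 |
| 5% | 20% | 100% | 4.0% | 30 × 0.05 × 0.20 × 1 = 0.30 |

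If *w* and *s* are the same in both arms, the risk difference shrinks by the factor 1 − *w* × *s*, that is by 0.985 (1 − 0.03 × 0.5) at one end and 0.80 (1 − 0.20 × 1) at the other.

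**If withdrawn subjects are dropped.** Suppose one treated patient in an arm has a device-related event, is withdrawn for it, and is replaced by a patient without an event. Keeping both gives 1/31 = 3.2%; dropping the first gives 0/30 = 0%. The documents give no basis for saying how often this would happen.

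**Precision when unknowns are not counted as No.** With no events among *n* subjects of known status, the exact two-sided 95% upper limit is 1 − 0.025^(1/*n*): 11.6% at *n* = 30, 12.8% at *n* = 27 and 14.2% at *n* = 24. The last two would apply only if known-status numbers fell that far; replacement works against that.

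**The case against.** The strongest reply is the replacement rule. If the 60 completers are the analysed set, and completion means reaching the one-month visit, a subject who leaves on day 2 never enters the 30-day rates. That reading is natural and part of it stands: it is not established that a short observation will be counted as a 30-day No. It does not remove the problem, however. No section says that withdrawn subjects are left out; the only stated ground for exclusion from analysis is a major protocol deviation, judged case by case. The instruction to collect their full data suggests possible use. Leaving them out would also be informative, because adverse event is itself a withdrawal reason.

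Three stronger readings are tempting, and the documents do not support them.

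- *The plan scores unknown status as No.* Nothing directs this, and the item could be left blank. The rule and the form together permit it.
- *The plan contradicts itself on when data collection ends, so everyone's data stop at discharge.* The phrase *this point* in Steps and Procedures is vague, but it closely follows the instruction to complete the sheet for each post-operative period, and that sheet has a 30-day block. Study Details and the outcome definitions also point to a month. If discharge were meant for all, with *s* = 50% to 80%, a true 3% risk would appear as 1.5% to 0.6%, with 0.45 to 0.72 events missed per arm. Those figures rest on a strained reading and should not be used as the size of the problem. A part of the protocol directly after Steps and Procedures was not in the text available to me, so I cannot say whether it settles the matter.
- *One missed leak is an arm's whole result.* At an assumed risk of 1% to 3%, 0.3 to 0.9 leaks are expected among 30 patients, and one leak is 3.3 percentage points. But the loss occurs only if the leak arises after last contact, in an early withdrawal who is still analysed.

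It is also fair to say that the plan attaches no non-inferiority margin to these outcomes.

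**Conclusion.** The point holds as a possibility that the plan leaves open. Following the withdrawal rule can put a status from a few days into a 30-day field, and the form would not show it. Dropping the same subjects could remove adverse-event withdrawals from the rates. Either way the 30-day figures can be too low.

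The reach is limited to two secondary outcomes, leak requiring intervention and device-related adverse events. The intraoperative bleeding outcome is untouched. Through early recording, the expected loss is about 0.0045 to 0.30 events per 30-patient arm; this rests wholly on assumed values of *p*, *w* and *s*. The exclusion route cannot be sized from the documents. The change is worth making because it is cheap and because contact dates that were never recorded may be hard to recover later.

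**What to change.** 1. **Withdrawal of Subjects:** close in-hospital items at withdrawal. Complete the 30-day leak and device-event items at day 30 from the routine follow-up record, unless the subject withdraws consent for use of records.
2. **Appendix C, 30-day block:** add *Date assessed* and *Unknown*. Do not count *Unknown* as *No*; report its number by arm.
3. **Statistics:** state that randomised, treated subjects who withdraw stay in the 30-day safety analysis alongside their replacements.
4. **Steps and Procedures:** replace the undefined end of data collection with a statement that it follows the 30-day evaluation, in line with Study Details and Secondary Outcome Measures.

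The cost is protocol and form wording, and a chart look-up for the few withdrawn patients. No visit is added, since routine follow-up continues under the practice's own regimen. The denominator with known status will be slightly smaller than if every unknown were counted as *No*.

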**Primary Outcome Measure:**

- Incidence of intraoperative staple line bleeding from endoscopic or laparoscopic images as measured by the provided bleeding severity scale

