### **Steps and Procedures:**

The study will include 60 total consecutive cases, randomized for stapler type: 30 with the AEON™ Endostapler and 30 with Endo GIA™ Reloads with Tri-Staple™ Technology. Surgeries will be performed by [name].

All patients will undergo the standard preoperative evaluation pathway. Patients must sign informed consent for the operation.

All firings with the AEON™ Endostapler will be done with THICK MODE for the purposes of this study and shall conform to the AEON™ Instructions for Use. All firings with the Endo GIA™ Reloads with Tri-Staple™ Technology and Ultra Universal Handle should be done according to the Endo GIA™ Instructions for Use.

To measure incidence and degree of staple line bleeding, a third-party blinded evaluator will be used. No sutures, cautery or clips shall be applied during stapling for staple line bleeding, unless required at surgeon's discretion. Following the last firing, a member of the surgical or nursing team or the research coordinator present for the case will count 10 seconds and then capture images with the laparoscope. If bleeding from the staple line requires control prior to the last firing, an additional image should be captured before applying sutures, cautery, clips, etc. Five pictures will be obtained from each case: the pylorus, distal sleeve near the distal end of the staple line, mid-sleeve at the incisura angularis, proximal sleeve and GEJ near the proximal end of the staple line. These photographs will be sent by the research coordinator to the third-party evaluator either electronically or by mail. The third-party evaluator will be blinded to the device of each case. Upon receipt of photographs, the evaluator will evaluate staple line bleeding according to a provided Bleeding Severity Scale for Laparoscope Images (Appendix A) and record results in the Bleeding Severity Evaluation Sheet (Appendix E).

At the end of each case, the surgical team will fill out the relevant sections of the Data Collection Sheet (Appendix C).

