**Statistics:**

This is an open-label study (since the patient will be blinded and the evaluation for the primary outcome will be done by a third party blinded to the stapler used). Formal sample size calculations were not performed as the purpose of the study is to demonstrate non-inferiority. The number of subjects was chosen based on feasibility and is considered sufficient to meet the study objectives.

Detailed methodology for summary and statistical analyses of the data collected in this study will be documented in the Clinical Study Report. T-test and chi-square test will be used for univariate analysis of continuous and categorical data respectively. Regression analysis may be used to identify the independent effect of several parameters on primary or secondary outcomes if there are statistically significant differences in univariate analysis.

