## Appendix E – Bleeding Severity Evaluation Sheet

Evaluation Date: \_\_\_\_\_ Evaluator: \_\_\_\_\_

Case #	Staple Line Image from Laparoscope	Staple line bleeding per Bleeding Severity Scale (choose one):				
		No bleeding	Minimal bleeding	Moderate bleeding	Excessive bleeding	Profuse bleeding
	A. Pylorus	1	2	3	4	5
	B. Distal sleeve near distal end	1	2	3	4	5
	C. Distal sleeve	1	2	3	4	5
	D. Proximal sleeve	1	2	3	4	5
	E. GEJ near proximal end	1	2	3	4	5

Case #	Staple Line Image from Endoscope	Staple line bleeding per Bleeding Severity Scale (choose one):				
		No bleeding	Minimal bleeding	Moderate bleeding	Excessive bleeding	Profuse bleeding
	F. Pylorus	1	2	3	4	5
	G. Distal sleeve near distal end	1	2	3	4	5
	H. Distal sleeve	1	2	3	4	5
	I. Proximal sleeve	1	2	3	4	5
	J. GEJ near proximal end	1	2	3	4	5

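### The Summary and the Primary Outcome Measure section name different primary outcomes, and no rule ranks or combines the laparoscopic and endoscopic bleeding scores

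*Combined protocol and SAP*

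**What the plan says.** - **Summary:** "Stapler performance will be evaluated primarily by incidence and degree of staple line bleeding from endoscopic images", graded by a blinded third party.
- **Primary Outcome Measure:** "Incidence of intraoperative staple line bleeding from endoscopic or laparoscopic images as measured by the provided bleeding severity scale". Degree is not named.
- **Steps and Procedures:** five laparoscopic pictures are graded on the Appendix A scale and five endoscopic pictures on the Appendix B scale. The paragraph on the laparoscopic pictures speaks of both incidence and degree. The determination of bleeding is "based on the picture with the highest bleeding severity score for laparoscopic and endoscopic evaluation separately".
- **Appendix E:** every picture is graded 1 to 5, and grade 1 is labelled as no bleeding. Rows A-E are laparoscopic and rows F-J endoscopic. There is no row for a patient-level or combined score.
- **Secondary Outcome Measures:** neither view, and no bleeding grade, is listed for comparison between the arms.
- **Statistics:** "the purpose of the study is to demonstrate non-inferiority". The t-test and chi-square test are assigned by data type, and neither is tied to the primary outcome. "Detailed methodology for summary and statistical analyses of the data collected in this study will be documented in the Clinical Study Report".
- **Early control (Steps and Procedures):** if bleeding needs control before the last firing, "an additional image should be captured before applying sutures, cautery, clips, etc". Gastroscopy comes before clipping "unless for circumstances judged by the surgeon to be medically necessary to do so before the endoscopy".

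**The concern.** The two statements of the primary outcome differ on the measure (incidence, or incidence and degree) and on the image source (endoscopic, or endoscopic or laparoscopic). The procedures then produce two scores per patient and leave them unranked. A trial of 30 per arm can therefore report several different primary results, each defensible from the text. The only place promised for the detailed methods is a report written after the data exist. A non-inferiority claim is credible only if the variable behind it was fixed beforehand.

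**Working it through.** **1. The sections side by side.**

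| Section | Measure | Image source |
|---|---|---|
| Summary | Incidence and degree | Endoscopic |
| Primary Outcome Measure | Incidence | Endoscopic or laparoscopic |
| Steps and Procedures, laparoscopic paragraph | Incidence and degree | Laparoscopic |
| Steps and Procedures, scoring rule | Worst picture | Each view separately |
| Statistics | Not stated | Not stated |

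Reading endoscopic in the Summary loosely, to cover both views, removes the conflict over source. The conflict over degree remains.

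**2. Candidate primary variables.** There are two measures (incidence, grade) and three sources (laparoscopic, endoscopic, worst of both), so 2 × 3 = 6 readings. Take a patient whose worst laparoscopic grade is 3 and worst endoscopic grade is 1. That patient is an event on the laparoscopic view and on a composite, and a non-event on the endoscopic view. The sections do not settle which.

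**3. Cut-off for incidence.** None is stated. Because Appendix E labels grade 1 as no bleeding, grade 2 or higher is the natural definition. This settles the cut-off but not the view.

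**4. Size, as illustration.** The plan gives no figure to reproduce: it states no alpha, margin, bleeding rate or correlation. Assume a one-sided 2.5% test on each view, both true differences exactly at the margin, and a claim supported by success on either view. With z = 1.96 and r the correlation between the two test statistics:

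Error = 1 − P(Z1 < 1.96 and Z2 < 1.96)

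- r = 0: 1 − 0.975² = 4.94%
- r = 0.3: 4.76%
- r = 0.5: 4.54%
- r = 0.7: 4.17%

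The same formula gives 3.5% at r = 0.9, so 4.2-4.9% is a range for r between 0 and 0.7 and not a bound.

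**5. Event rate of a composite.** Assume 40-70% bleeding per view. With independent views at 70%, the either-view rate is 1 − 0.3² = 91%. At 40% per view and a latent correlation of 0.7 it is 52%.

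**6. Precision at 30 per arm.** The half-width of the 95% CI is 1.96 × √(2p(1 − p)/30). This is 23.2 points at p = 0.3 or 0.7, 25.3 at p = 0.5, and 14.5 at p = 0.91.

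**7. Early-control image.** The additional image is ordered in the same paragraph that sends the photographs to the evaluator, and the scoring rule takes the highest-scored picture. Appendix E has no row for it, however, and nothing carries it into the endoscopic score when clipping came before gastroscopy.

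**The case against.** The best case for the plan is that the Primary Outcome Measure section is the formal statement and the Summary only a paraphrase. On that view the word joining the image types means bleeding seen on either, Appendix E supplies the cut-off, and the worst picture is taken separately only because the two views use different picture scales. This is a reasonable reading, and it is why a composite is the default in the fix. But no section states it, the Summary contradicts it on source and on degree, and the scoring rule stops at two scores.

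A reader might infer three stronger things that the documents do not support.

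- **That the result was, or will be, selected after the fact.** The text shows only that nothing prevents it.
- **That the two views would often contradict each other.** Simulations with identical devices do show this: opposite signs in 24-41% of trials, and different non-inferiority verdicts in 26-50% at assumed margins of 15-30 points. These figures depend on assumed bleeding rates of 40-70% and correlations of 0 to 0.7. They mostly reflect sampling noise, which would be there even with one view prespecified. They are not bounds: opposite signs fall to about 15% at correlation 0.9 with equal rates. The verdict figure also needs a margin that the plan lacks.
- **That early-controlled bleeding drops out of the primary result.** The wording suggests the additional image reaches the evaluator. Early clipping is recorded in Steps and Procedures, on the Appendix C sheet and as a secondary outcome. What stands is the missing row and the missing rule for the endoscopic score.

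**Conclusion.** The point holds as a contradiction about the primary outcome, together with a missing rule for two scores per patient; it is more than missing detail. The conclusion rests on the text available for review and needs no calculation. Its possible effect on error, from 2.5% to 4.2-4.9%, is illustrative. It applies only if success on either view is accepted, both true differences lie at an assumed margin, and the test statistics correlate between 0 and 0.7. The early-control image is a separate and smaller scoring gap. The plan should be corrected before any data review.

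**What to change.** **Primary variable.** Before any data review, make the Summary, Primary Outcome Measure, Steps and Procedures and Statistics sections agree on one variable:

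- Measure: incidence, defined as a worst grade of 2 or higher.
- Source: by default a composite of grade 2 or higher on either view, which is closest to the formal definition; otherwise one named view.
- Analysis: risk difference with a 95% CI.
- Secondary: each remaining view and the 1-5 grade, with the grade analysed by an ordinal method (Wilcoxon or proportional odds).

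**Additional image (minor).** Add a row to Appendix E. State that its blinded grade counts in the worst-picture score and in the primary incidence, including when clipping preceded gastroscopy. This concerns scoring only, not when bleeding is controlled.

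**Cost.** The change needs wording in four sections, one form row and a clinical decision on which view matters. It needs no new patients, and the pictures are already planned. There are three downsides:

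- Degree becomes secondary.
- A yes/no outcome generally has less power than an ordinal test. Under assumed grade distributions, and for detecting a difference rather than for non-inferiority, the loss is about 4-21 points at odds ratio 2.5 and 2-8 points at 0.4.
- A composite raises the event rate. At 91% a true increase cannot exceed 100 − 91 = 9 points, so a margin would have to be set with the expected rate in mind.

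The non-inferiority margin is still missing. That is a separate matter which this change does not resolve.
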